## 8. Safety analyses

### 8.1. Safety analysis population

For the analysis of safety outcomes, all patients who effectively received any drug (i.e. at least one treatment dose) are included in the safety analysis in the intervention group they actually received (all-patients-treated approach).

## 8.2. Safety outcomes and analyses

### 8.2.1. *Serious adverse events*

*General aspects:* Serious adverse events (SAEs) will be coded using the Medical Dictionary for Regulatory Activities (MEDDRA) and will be reported based on MEDDRA preferred terms and body systems. All SAEs will be analyzed based on counts of patients with a specific category and not on counts of individual adverse events. The relationship between SAEs and treatment is determined by the local investigator and categorized as "drug-related" if possibly, probably or definitely related to treatment.

The following summaries will be present by treatment group:

- a. description of all deaths of patients up to 12 months after treatment stop;
- b. the total number of patients with any SAE by preferred term and body system up to 12 months after treatment stop;
- c. the total number of patients with any drug-related SAE by preferred term and body system up to 12 months after treatment stop;

Statistical tests of association, using logistic regression, adjusted for hospital and stratum (new/ retreatment case), between treatment and occurrence of SAE will be performed for the following categories:

- a. number (%) of patients with any SAE, any drug-related SAE;
- b. number (%) of patients with the most common SAEs and drug-related SAEs (most common: with an incidence of 10% or more in at least one treatment group).

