Effective TB control is through detection and treatment of active cases. Treatment requires a combination of drugs and long duration (regimens of at least 6 months). The main first-line drugs are rifampicin and isoniazid, and resistance to both defines MDR-TB which proves impossible to cure with these and other first-line drugs (pyrazinamide, ethambutol, streptomycin). MDR-TB treatment is far more difficult and needs second-line drugs. Among the greater variety of these drugs only a few are sufficiently active, i.e. the later generation fluoroquinolones (mainly gati- and moxifloxacin) and the 2nd-line injectables (2LI). If MDR-TB develops resistance to these two groups as well, an ultra-resistant form develops called XDR-TB; with only one of both groups resistant this is called pre-XDR-TB. MDR-TB treatments are difficult, toxic, expensive and yield highly unsatisfactory results in almost all NTPs. In the DF area, a short and highly effective MDR-TB treatment was developed and has been used with very good results for already 10 years (see further).

The International Union against Tuberculosis and Lung Disease (Union) and the WHO recommend a cascade of TB treatment regimens each aiming at very high but not 100% effectiveness, while allowing a small percentage of failure and relapse cases to start the next regimen in the cascade. The switch to the next higher [sequentially used and “higher” in complexity] regimen is meant to be made as early as possible. In practice this switch is often made too late, since it depends on careful microscopy to identify suspects in need of rapid drug susceptibility testing, and their efficient referral. Particularly patients with MDR-TB may die, default or acquire resistance to more drugs before being recognized as having MDR-TB and put on an appropriate treatment regimen. For some patients with extensive disease and patients with HIV infection, 6 months of the standard primo-treatment (Cat. 1) is too short, leading more frequently to relapse. The current standard first-line

drug retreatment regimen (Cat. 2) is more toxic but not more effective for MDR-TB than the current Cat. 1, and it has only a marginal advantage for other types of drug-resistant TB at the risk of amplification of resistance.

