4.2 Inclusion and exclusion criteria

In order to be eligible, study participants **must meet the following criteria**:

- Diagnosed with smear-positive pulmonary TB
- 15 years or older
- Able and willing to provide written informed consent

Potential participants meeting any of the following criteria **will not be enrolled in the study**:

- contacts of MDR-TB patients and other MDR-TB suspects diagnosed with resistance on rapid DST for rifampicin performed prior to start of treatment according to NTP guidelines
- smear-negative pulmonary and extra-pulmonary TB cases
- patients in need of hospitalization because of very bad general condition or complications
- patients with clinically active liver disease, for the study defined as jaundice confirmed by a local Medical Officer (Government)
- any known HIV-positive patient (although none are expected)
- any patient with known hepatitis B or C infection
- pregnant women; in addition, patients in the intervention arm who become pregnant during treatment will be switched to the control arm

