Unknown :	The outcome of the AE is not known because the patient did not return for follow-up (lost to follow-up)

All SAEs will be compiled by the clinic supervisor on the paper report form for the corresponding visit, and completed by the Medical Officer in charge of the hospitalization as appropriate. The Investigator will systematically check and validate the paper records on SAE and other points during his supervision visits to clinics and hospitals, and correct / complete as required before entering the data in the electronic CRF. SAE will be registered as soon as treatment has started and up to its end.

There may be situations when an SAE has occurred and the investigator has minimal information to include in the initial report to the pharmacovigilance. However, it is very important that the investigator always makes an assessment of causality for every event prior to transmission of the report to the pharmacovigilance. The investigator may change his/her opinion of causality in light of follow-up information, amending the SAE-report form accordingly.

All SAE's whether or not deemed drug related or expected must be reported immediately or within 24 hours (one working day) using the SAE Notification Form by telefax or email to:

Clinical Trials Unit
Institute of Tropical Medicine
[name]
[name]
[contact]
Email: [contact]

The title of the e-mail/fax should mention the name of the study code, the patient code and the wording “SAE – Initial/follow up report”.

Line listings of all reported SAE's will be sent at least quarterly to the DSMB, and on a yearly basis to the IRB of the Union, ITM and the EC of UZA. They will also be sent yearly to the study coordinator in Bangladesh to submit these to the respective Authorities and/or ECs.

The Principal Investigator is responsible to report the SAE to the relevant Institutional Ethics Committees and the Bangladesh Regulatory Authorities immediately or according to the deadline established by each Ethics Committee.

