#### 4.2. Efficacy study endpoints

##### *Primary endpoint*

The primary efficacy endpoint is the incidence of adverse treatment outcomes. Following the WHO guidelines from 2010, as currently in use in the NTP in Bangladesh, an adverse treatment outcome is defined as any occurrence of the following:

- Relapse: Cured previously from TB or completed treatment for TB and now having bacteriologically positive sputum for TB (at 12 months follow-up or at an earlier time point)
- Default: The patient whose treatment was interrupted for 2 consecutive months or more.

- Failure: Sputum positive for TB at 5 months or later during treatment. Failure will also be declared if the regimen has to be changed for at least 2 drugs due to adverse events.
- Death: All-cause mortality between case registration and end of TB treatment (related or not to TB or TB treatment)

Patients who are transferred out will be excluded from the outcome analysis.

In line with current WHO recommendations, patients detected with MDR-TB or rifampicin resistance before any outcome applies and switched to the MDR-TB regimen will be excluded from the outcome analysis.

Analyses will be performed using the NTP smear-based recurrence (failure, relapse) definitions, but as a secondary approach culture-based definitions will be used. In each analysis, if a patient has two events for the analysis of interest, the first endpoint will be taken into account, except for cured/completed followed by relapse which is considered as relapse.

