### 8.2.2. *Grade 3-4 Liver Toxicity*

The total number of patients with grade 3, grade 4 and grade 3-4 liver toxicity up to 12 months after treatment stop will be presented. Statistical tests of association, using logistic regression, adjusted for hospital and stratum (new/ retreatment case), between treatment and liver toxicity will be performed.

Due to the multiplicity of tests performed, the statistical tests of association between treatment and safety outcomes will not be interpreted as definite proof of more or less harm of any of the treatment but will be used as a screening tool. The use of a statistical tests will allow the exclusion of any observed difference which may be due to chance.

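### The safety counts run to 12 months after treatment stop with no cut at a regimen change and no rule for patients who took regimens in sequence

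*SAP*

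**What the plan says.** **Window.** SAP 8.2.1 counts "the total number of patients with any SAE by preferred term and body system up to 12 months after treatment stop", with the same limit for deaths and drug-related SAEs. SAP 8.2.2 counts "grade 3-4 liver toxicity up to 12 months after treatment stop". Treatment stop is not defined: it could mean the end of the first regimen or of the last one taken.

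**Grouping.** Under SAP 8.1, all patients with at least one dose "are included in the safety analysis in the intervention group they actually received". No rule covers a patient who received one regimen and then another.

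**Routes to other drugs.**
- Protocol 2.1 moves any patient found to have MDR-TB to a nine-month regimen that, as listed, contains no rifampicin.
- Protocol 5.3 restarts rifampicin-sensitive failures and relapses on Cat. 1 in the intervention arm (high-dose, per Protocol 5.1) and on Cat. 2 in controls.
- Protocol 4.2 states that "patients in the intervention arm who become pregnant during treatment will be switched to the control arm".

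**Efficacy, by contrast.** SAP 4.2 says that patients found resistant before any outcome applies and "switched to the MDR-TB regimen will be excluded from the outcome analysis". SAP 4.1 counts a patient who takes a second regimen by the outcome of the first. Safety has no matching rule.

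**Collection.** Protocol 7.1 says: "SAE will be registered as soon as treatment has started and up to its end". The schedule in Protocol 5.1 shows no adverse event collection at the visit 12 months after treatment, and liver tests only at enrolment, weeks 2 and 4 and month 2.

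**The concern.** The pilot asks whether double-dose rifampicin adds toxicity. Protocol 2.1 and 8 and SAP section 1 make a lack of excess toxicity a condition for going on to the cluster-randomised study. If the count continues after a patient has left the first regimen, events caused by other drugs enter that comparison.

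Liver toxicity shows this within the scheduled tests. A patient switched soon after week 2 has the week 4 and week 8 tests on the MDR regimen, so shortening the 12-month window would not by itself solve the problem.

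The grouping rule adds a second difficulty. When a patient has had two regimens, someone must choose a group, and as the plan stands that choice could be made after the data are seen.

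**Working it through.** **1. The plan's own safety figure (Protocol 8.4).** Inputs: hepatitis 1.5%, an increase of 2 percentage points, 500 per arm.
- 1.5% x 500 = 7.5 and 3.5% x 500 = 17.5, rounded to 8 and 18.
- Pooled proportion = 26/1000 = 0.026. Standard error = sqrt(0.026 x 0.974 x 2/500) = 0.01007.
- z = 0.020/0.01007 = 1.99, two-sided p = 0.0469. The stated 0.047 is reproduced.

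**2. How far one event moves it (same formula).**

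| Control v intervention | p |
|---|---|
| 8 v 18 | 0.047 |
| 9 v 18 | 0.079 |
| 8 v 17 | 0.068 |
| 8 v 19 | 0.032 |

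**3. MDR switches.** Protocol 8.4 expects about 10 resistant cases in each arm. The documents give no number switched and no SAE rate on the MDR regimen, so these are assumptions: 10 switched in the intervention arm; 10, 5 or 0 in control; SAE risk r after the switch of 5-30%.
- Net (intervention minus control) = (10 - control switches) x r.
- Range: (10 - 10) x r = 0, up to (10 - 0) x 0.30 = 3 patients, or 3/500 = 0.6 percentage points.

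**4. Second courses.** From Protocol 8.4, control failures and relapses are (2% + 2%) x 500 = 20. Half are culture-positive (10), and about half of those are resistant (5), leaving 20 - 5 = 15 for a second course. Assume 10-15 in the intervention arm and the same 5-30% risk.
- Net = (10 to 15 - 15) x r. Range: -5 x 0.30 = -1.5, up to 0.

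**5. Combined net (intervention minus control).**

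| MDR switches, int. v control | Second courses, int. v control | r = 5% | r = 30% |
|---|---|---|---|
| 10 v 10 | 10 v 15 | -0.25 | -1.5 |
| 10 v 10 | 15 v 15 | 0 | 0 |
| 10 v 5 | 10 v 15 | 0 | 0 |
| 10 v 5 | 15 v 15 | +0.25 | +1.5 |
| 10 v 0 | 10 v 15 | +0.25 | +1.5 |
| 10 v 0 | 15 v 15 | +0.5 | +3.0 |

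The range is about -1.5 to +3 patients. A count cut at the first regimen change makes this contribution zero by construction.

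**6. The two windows.** The SAP counts SAEs to 12 months after treatment stop; Protocol 7.1 registers them to the end of treatment. The SAP table therefore covers a year in which the protocol plans no SAE registration and, for liver toxicity, no scheduled test.

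**The case against.** **The direction is not shown.** A reader might infer that, because the intervention is meant to switch resistant patients early, MDR-regimen toxicity will show up as double-dose rifampicin toxicity. The documents do not support that. About 10 resistant cases are expected in each arm, and control resistance is also sought at months 2, 3 and 5, at the end of treatment and at relapse. In a long window, late switches count as much as early ones. Second courses push the other way, if anywhere. This objection stands.

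**Many second courses barely enter.** Active relapse detection is at the visit 12 months after treatment. If treatment stop means the end of the first regimen, a course begun there starts as the window closes. The 15 control patients are therefore an upper bound. This also stands; failures during treatment remain inside.

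**The later drugs may not be very toxic here.** Protocol 1.1 says "MDR-TB treatments are difficult, toxic, expensive and yield highly unsatisfactory results in almost all NTPs", but goes on to say that the project area has used a short regimen with very good results. The quoted sentence is no measure of SAE risk in this trial.

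**Safeguards exist.** Admission for the MDR intensive phase is not an adverse event, Protocol 7.1 judges causality against the study drug, drug-related SAEs are shown separately, and SAP 8.2.2 calls the tests a screening tool. These help in part, but the any-SAE count ignores causality, and SAP 8.2.1 defines drug-related by reference to treatment in general.

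**A strategy-level count is legitimate.** The synopsis hypothesis joins the double dose to early monitoring and switching, and stopping the count at an arm-dependent switch shortens follow-up selectively. This is a good reason to keep the unrestricted count. It does not remove the need for one that isolates the first regimen.

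**Conclusion.** The gap is real and lies in the text: no cut at a regimen change, no definition of treatment stop, and no rule for regimens taken in sequence, although the efficacy sections deal with both MDR switches and second regimens. It would be wrong to say that the SAP charges later events to the randomised arm, since it groups by treatment received; the difficulty is that this rule does not settle where a patient with two regimens belongs.

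Neither sign nor size can be derived from the documents. The range of about -1.5 to +3 patients rests on assumed switch numbers and SAE risks, and its upper end requires that no resistant control patient is ever switched. The hepatitis contrast serves only for scale. It is not the composite safety endpoint, and Protocol 8.1 asks for p-values to be read with care. Still, a single event can carry that contrast across 0.05, so the allocation rule should be fixed in advance. The mismatch between the SAP window and the protocol's SAE registration needs no assumption.

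**What to change.** In SAP 8.1-8.2:
- Assign each patient to the regimen of the first dose, and define treatment stop as the end of that first regimen.
- Report SAEs and grade 3-4 liver toxicity from first dose to the earliest of the end of that regimen, start of the MDR regimen, start of a second course, or change to the other arm's regimen.
- List later events separately, by the regimen being taken when they occurred.
- Show the unrestricted count alongside, labelled as the strategy-level result.
- Reconcile the 12-month window with the SAE registration period in Protocol 7.1 and the schedule in Protocol 5.1.

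No treatment rule changes. The cost is SAP wording and two extra tables. Late events of the first regimen move to the listing, and follow-up is slightly shorter for the few patients who switch. For retreatment cases the first regimen lasts 8 months in controls and 6 in the intervention arm, so time at risk should be shown beside the counts.

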4.3 Sample size

The sample size selected is 1000 patients (500 randomized to intervention, 500 to control). The study will be conducted in eight DF Bangladesh outpatient clinics with an LED TB fluorescence microscopy laboratory that register about 2000 TB cases per year of which 65% are smear-positive pulmonary TB (new or retreatment). Enrolment will target 1000 randomised smear-positive pulmonary TB patients. Given an expected 5% refusal rate, it is expected that recruitment will require 9-10 months.

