8.4 Sample size and power

The sample size of two times 500 patients is a trade-off between precision and exposing an excessively high number of patients to potentially more toxic treatment. Power has not been taken into account, but if the results are favourable large scale cluster-randomized study will be designed to bring definitive proof.

The registered incidence of clinically apparent hepatitis from any cause during TB treatment is 1.5% for the study population. With the proposed sample size, an increase by at least 2% compared to the control arm will attain statistical significance ($p=0.047$).

With the standard (=control) regimens and definitions, about 2% failures and 2% relapses are currently notified by the DF project, but only 50% of those are culture-positive, and about half of the culture positive failures and relapses are rifampicin-resistant. Overall cure rate (new and retreatment cases together) is close to 90%, with 4% default and 4% deaths. Based on the data from 2010 about 20 cases with rifampicin resistance may be enrolled, 10 in each arm. We estimate that the more effective study regimen plus early detection of serious drug resistance rolled over to MDR-TB

treatment will prevent drug resistant failure and relapse, reduce rifampicin susceptible relapse to an estimated two third, and reduce death and default because of unrecognized rifampicin resistance to 80% of the control arm. This total estimated reduction of unfavourable outcome from 10% to 7% remains non-significant with the targeted enrolment of two times 500 cases. With 80% power and 95% confidence level, 2 x 1421 patients would have to be enrolled, which is not feasible and also difficult to justify. However, a slightly larger reduction of unfavourable outcome from 10% to 6.5% comparing two arms of 500 cases each would already result in a significant p-value. Additional evidence will be obtained studying *rpoB* mutations, initially (all smear-positives) and at time of failure or relapse (only in the few such cases expected). Absence of low-level resistance mutations only among patients with unfavourable outcome on the high-dose arm, while they were present among new cases in both arms, will be interpreted as additional evidence of effectiveness of the increased dosing.

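### SAP 8.2.1 tests single SAE terms only from 10% in an arm, so clinically apparent hepatitis is tabulated but never compared between arms under its own definition

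*SAP*

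**What the plan says.** SAP 8.2.1 plans two groups of logistic regression tests, adjusted for hospital and stratum.

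- Group (a) has no incidence threshold: "number (%) of patients with any SAE, any drug-related SAE".
- Group (b) covers individual SAEs and drug-related SAEs, but only common ones: "most common: with an incidence of 10% or more in at least one treatment group".

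The same section tabulates all SAEs and all drug-related SAEs by treatment group, preferred term and body system, with no threshold. SAP 8.2.2 adds adjusted logistic tests of association "between treatment and liver toxicity will be performed", also without a threshold. The event there is grade 3-4 toxicity, which SAP 4.2 defines by transaminase cut-offs. SAP 8.2.2 calls the safety tests a screening tool.

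Protocol 8.4 uses a different liver event: "The registered incidence of clinically apparent hepatitis from any cause during TB treatment is 1.5% for the study population". It says that an increase of at least 2 percentage points over control would be significant at the planned size, with p = 0.047. For deaths it states: "Overall cure rate (new and retreatment cases together) is close to 90%, with 4% default and 4% deaths". Protocol 4.3 sets 500 patients per arm.

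**The concern.** Absence of excess toxicity is the first criterion listed for going on to the larger cluster-randomised trial (protocol 2.1 and 8; SAP 1). The one safety event for which the protocol gives both a control rate and a difference of interest is clinically apparent hepatitis. Suspected liver damage leads to referral for hospitalisation, and hospitalisation is an SAE criterion (protocol 7.1), so most such cases would be SAEs and would belong in group (b). If the gate cannot open at the rates the protocol expects, the term-specific screen adds nothing. The event that protocol 8.4 discusses would then be read from a table without an estimate of the difference.

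**Working it through.** **Inputs.** 500 per arm (protocol 4.3). Hepatitis 1.5% in control and 1.5% + 2 points = 3.5% with the increase; deaths 4% (protocol 8.4). Gate 10% (SAP 8.2.1). Two-sided alpha 0.05 is assumed, from the 95% confidence level used in protocol 8.4.

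**1. The protocol's own figure.** Expected counts are 0.015 × 500 = 7.5 and 0.035 × 500 = 17.5, rounded up to 8 and 18. The pooled proportion is 26/1000 = 0.026.

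- SE = √(2 × 0.026 × 0.974 / 500) = 0.01006
- z = 0.020 / 0.01006 = 1.99, two-sided p = 0.047

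This reproduces the stated value with an uncorrected chi-square test. Fisher's exact test on the same counts gives p = 0.072.

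**2. Can the gate open?** The gate is 0.10 × 500 = 50 patients. That is 50/17.5 = 2.9 times the expected number with hepatitis at the increased rate, and 2.5 times the 20 expected deaths per arm. The exact binomial probability that one arm reaches it, P(X ≥ 50) with n = 500, is:

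| True rate | P(X ≥ 50) |
|---|---|
| 1.5% | 2e-25 |
| 3.5% | 6e-11 |
| 4% | 5e-9 |
| 6% | 0.0003 |
| 7% | 0.008 |
| 10% | 0.52 |

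The rule asks for either arm. That at most doubles these figures when both arms share the rate, for example to 1e-8 for deaths at 4%.

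**3. How well do the ungated tests cover hepatitis?** A hepatitis-specific test of 1.5% against 3.5% has this power, using the mean rate 0.025 for the null variance:

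- null SE = √(2 × 0.025 × 0.975 / 500) = 0.00987
- alternative SE = √((0.015 × 0.985 + 0.035 × 0.965) / 500) = 0.00985
- power = Φ((0.020 − 1.96 × 0.00987) / 0.00985) = Φ(0.066) = 53%

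In the any-SAE test the same excess is diluted by other SAEs. The documents give no rate for these, so a range is assumed, equal in both arms and independent of hepatitis. The arm rate is then 1 − (1 − b)(1 − h), where b is the background rate and h the hepatitis rate.

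| Assumed other SAEs | Any SAE, control vs intervention | Power |
|---|---|---|
| 0% | 1.5% vs 3.5% | 53% |
| 2% | 3.5% vs 5.4% | 32% |
| 4% | 5.4% vs 7.4% | 24% |
| 6% | 7.4% vs 9.3% | 19% |
| 10% | 11.4% vs 13.2% | 14% |

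The grade 3-4 test in SAP 8.2.2 is closer, but its event is a transaminase level. Scheduled liver tests are at weeks 0, 2, 4 and 8 only (protocol synopsis and 5.1), whereas the double dose runs to month 6 (protocol 2.1). Clinical hepatitis below the cut-off, or later hepatitis without a liver test, is not in that count. The documents do not say how many cases this would be.

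**4. Which gate could open?** Probability that one arm reaches the gate:

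| Gate (patients) | True 1.5% | True 3.5% |
|---|---|---|
| 1% (5) | 0.87 | > 0.999 |
| 2% (10) | 0.22 | 0.98 |
| 5% (25) | 3e-7 | 0.05 |
| 10% (50) | 2e-25 | 6e-11 |

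**The case against.** The strongest reply is that little is lost. Protocol 8.1 puts description and estimation ahead of formal testing, and SAP 8.2.1 shows every SAE term by arm whatever its frequency. Only the term-level test is gated. The liver signal has several ungated routes: grade 3-4 toxicity in SAP 8.2.2, counted up to 12 months after treatment; the two pooled SAE tests; and the primary safety composite, analysed like efficacy under protocol 8.3.3. The monitoring board also reviews toxicity quarterly (protocol 7.2), and protocol 5.3 allows unscheduled visits with study procedures as needed. All of this stands, and it rules out several stronger conclusions that a reader might draw.

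- **That no specific SAE is set side by side between arms.** The tables by preferred term do exactly that.
- **That a hepatitis excess goes untested.** It is tested, through a related laboratory event and through pooled SAE counts.
- **That no SAE at all could reach 10%.** This is shown only for hepatitis and death, because the documents give no rate for any other term.
- **That the sample size rests on hepatitis.** Protocol 8.4 calls the size a trade-off and says power was not considered. The p-value of 0.047 illustrates what an observed difference would give at that size.

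A hepatitis-specific test would also have only about 53% power, so adding a p-value alone would settle little. This is a reason to ask for an estimate with an interval, which is also what protocol 8.1 favours. Finally, a low gate brings in sparse terms. At 5 versus 0 of 500, Fisher's p is 0.062 and the adjusted logistic model has no finite odds ratio. The choice of gate is a judgement and needs a matching method.

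**Conclusion.** The point holds in a limited form. At the rates in the protocol, the term-specific screen in SAP 8.2.1 is effectively empty: the chance that an arm reaches 50 of 500 is 6e-11 for hepatitis at 3.5% and 5e-9 for death at 4%. Clinically apparent hepatitis is tabulated and covered indirectly, but the SAP gives no between-arm comparison under the definition used in protocol 8.4. The gap is modest. It is worth closing because it concerns the first go/no-go criterion and the remedy is cheap.

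The gate result rests on 500 patients per arm and on the protocol's own rates. The loss of power in the any-SAE test rests on assumed background rates and independence, and shows direction and rough size only.

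**What to change.** In SAP 8.2.1:

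1. Name clinically apparent hepatitis during treatment as a category that is always compared between arms, with the difference in proportions and its 95% CI. State which recorded terms count.
2. Replace the 10% gate with one that can open at the protocol's rates, for example 1 to 2% in either arm (5 to 10 patients).
3. For sparse counts, specify score or exact intervals, or penalised logistic regression, in place of the standard adjusted model.

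As an illustration of item 1, 8 versus 18 of 500 gives a difference of 2.0 points. The simple SE is √((0.016 × 0.984 + 0.036 × 0.964) / 500) = 0.01004, so the 95% CI is 2.0 ± 1.96 × 1.004, or about 0.0 to 4.0 points. That tells the go/no-go decision more than a row in a table.

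The cost is SAP wording. Protocol 7.1 already has all adverse events recorded in the patient file. The SAP specifies coding for SAEs only, so it should be confirmed that any hepatitis managed without admission can be identified in the database. A few more exploratory comparisons result, and the screening caveat in SAP 8.2.2 already covers them.
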